5.4.2. Secondary Endpoints

1. 28-day, 56-day and 84-day PCR *Plasmodium* positivity rate for each *Plasmodium* species

2. Proportion of participants with confirmed malaria reported between day 0 and day 28 for each species
3. Description of epidemiological situation of malaria in the study areas from passive surveillance data.
4. Prevalence of *Kelch13* mutations and other genetic markers of antimalarial drug resistance of known functional significance.
5. Incidence of adverse events and serious adverse events by study arms during the course of prophylaxis.
6. Data on the place of residence, work, recent travel history and mobile phone use.
7. Detailed data and GPS mapping on a subset of participants and their peers relating to the behaviours and risk factors associated with malaria infection.
8. Overall prevalence of Plasmodium at baseline, stratified by season and risk factors.
9. Day 0, 28, 56 and 84 capillary blood levels of lumefantrine.
10. Prevalence of serological diagnostic markers of other infectious diseases.

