6.6. Follow-up

Participants will be asked to return for a follow-up assessment any time from 28 to 35 days after commencing prophylaxis. This will be regardless of the duration of their visit to the forest or the number of times they visited it in that period. At this assessment, they will be interviewed about how long they spent in the forest, where they went, why, who they travelled with and about risk factors for infection. Brief physical examinations, vital sign and symptom questionnaire will be performed. They will also be asked to report any diagnostic tests and/or treatment for malaria during the preceding 28-35 days.

Blood sampling at follow-up

At each follow-up visit, the following blood will be taken:

All individuals:

- Parasite PCR (Up to 1 ml).

- Dried blood spot for lumefantrine level (0.2 ml)

In those with confirmed clinical malaria at any time point between enrolment and follow-up:

- Dry blood blots (0.4 ml, 3 spots) collected on filter papers for:
 - o Parasite DNA genotyping for genetic markers of antimalarial resistance.
 - o Parasite whole genome sequencing and barcoding to identify geographical origin of parasites and compare genotypes to identify persistent infections.

In individuals who are planning to return again to the forest within the following 28 days after the follow up visit, they will be asked to continue their weekly prophylaxis according to the original treatment allocation on enrolment. They will then be asked to return for a second follow-up visit a further 28 to 35 days later when the above procedure will be repeated. This will be repeated one more time. If the person cannot be followed up within the scheduled period, e.g. because they do not return from the forest in time, then they will be followed up at the first opportunity and this will be recorded in the CRF.

Thus individuals may take prophylaxis continuously for a maximum of 3 periods of 28-35 days in the forest plus 4 weeks after returning totaling 112 days. The choice of study medication for each individual will follow the initial assignment on enrolment throughout the follow-up period.

In those who do not declare an intention to return to the forest within 28 days at any follow-up visit, no further follow-up visits will be offered at that time but they will be asked to complete 4 weeks of prophylaxis following their last day in the forest as post-exposure prophylaxis.

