8. SAFETY REPORTING

This trial will use drugs that have either been registered or evaluated extensively. To add to the evidence base for safety of AL as prophylaxis, we will record and review all Adverse Events (AEs) and Serious Adverse Events (SAEs) that are reported to occur in the study.

A symptom questionnaire will be performed on enrolment and at each subsequent follow-up visit to the health care center, to aid in the identification of adverse events. In addition, enrolled individuals will be encouraged to promptly report any unexpected symptoms or illnesses between follow-up visits to the study team.

The investigator is responsible for the detection and documentation of events meeting the criteria and definition of an adverse event (AE) or serious adverse event (SAE), as provided in this protocol.

All SAEs and AEs will be promptly documented from the moment of drug administration in the study to discontinuation of the participant from study participation. Any events occurring between screening and drug administration will be considered as baseline, preexisting conditions.

All adverse events must be recorded in the AE/SAE CRF. To avoid colloquial expressions, the adverse event should be reported in standard medical terminology. Whenever possible, the adverse event should be evaluated and reported as a diagnosis rather than as individual signs or symptoms. If a definitive diagnosis is not possible, the individual symptoms and signs should be recorded. Whenever possible, the aetiology of the abnormal findings will be documented on the CRF. Any additional relevant laboratory results obtained by the Investigator during the course of this study will be recorded on the CRF.

If the event meets the criteria for “serious”, the SAE must be reported to the PAL-Cambodia safety team within 24 hours from the time that the event was identified. If further data is required, additional documentation can be submitted. All SAEs must be followed until resolution, or until the SAE is deemed permanent or leads to death.

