8.1 Definitions

8.1.1. Adverse Event (AE)

An AE is any undesirable event or clinical deterioration that occurs to a study participant during the course of the study; that is, from the time of administration of study drugs until study ends (i.e., until the follow up visit) whether or not that event is considered related to the study drugs, or to a concomitant drug or procedure: e.g.

- any unfavourable and unintended symptom
- physical sign
- abnormal laboratory result
- an illness

Any new clinical sign or clinical deterioration that occurs between signing the consent form and the administration of study drugs is not an AE. This information will be recorded in the medical records, as a pre-existing condition.

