8.1.2 Serious Adverse Event

A serious adverse event is an AE that:

- results in death
- is life-threatening i.e. the participant was at risk of death at the time of the AE

- requires in participant hospitalisation or prolongation of existing hospitalisation
- results in persistent or significant disability/incapacity
- is a congenital anomaly/birth defect
- Any other significant medical condition

All of the above criteria apply to the case as a whole and should not be confused with the outcomes of individual reactions/events. More than one of the above criteria can be applicable to the one event. Important medical events that may not be immediately life-threatening or result in death or hospitalisation may be considered an SAE when, based upon appropriate medical judgment, they may jeopardise the participant or require medical or surgical intervention to prevent one of the outcomes listed in the definition above. Examples of such medical events include allergic bronchospasm requiring intensive treatment in an emergency room or at home, blood dyscrasias or convulsions that do not result in hospitalisation, or development of drug dependency or drug abuse.

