9.2.4 Adverse events

Adverse events will be graded according to Common Terminology Criteria for Adverse Events (CTCAE) Version 5.0 November 2017.

All adverse event summaries will refer to treatment emergent adverse events, i.e. adverse events that newly started or increased in intensity after the study drug administration. AE summaries will be generated for all AEs that occurred after study drug administration, until the end of the study.

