#### 4.4.5 Adverse events and serious adverse events by study arms during the course of prophylaxis.

Adverse events will be graded according to Common Terminology Criteria for Adverse Events (CTCAE) Version 5.0 November 2017.

All adverse event summaries will refer to treatment emergent adverse events, i.e. adverse events that newly started or increased in intensity after the study drug administration. AE summaries will be generated for all AEs that occurred after study drug administration, until the end of the study.

Incidence of adverse events and serious adverse events by study arms during the course of prophylaxis will be presented in the table 6a below. AE intensity and relationship to study drug wil be presented as in tables 6b and 6c. Graphical presentations might be considered when presenting these.

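### Protocol 8.1.1 closes the adverse-event and SAE period at the follow-up visit, although weekly study drug can be scheduled for up to four weeks after it

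*Protocol*

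**What the plan says.** **Definition.** Protocol 8.1.1 limits an adverse event to the time "from the time of administration of study drugs until study ends (i.e., until the follow up visit". Section 8.1.2 begins "A serious adverse event is an AE that", so the same limit applies to SAEs.

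**Visits and dosing.** Protocol 6.6 asks participants to return "any time from 28 to 35 days after commencing prophylaxis", however long they were in the forest. Appendix 1 agrees, with columns at D28-35, D56-63 and D84-91. Section 6.5 has weekly dosing continue during forest travel and for four weeks after leaving. For anyone who does not plan to go back within 28 days, 6.6 states that "no further follow-up visits will be offered at that time but they will be asked to complete 4 weeks of prophylaxis", counted from the last forest day.

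**Endpoint.** Protocol 5.4.2 lists "Incidence of adverse events and serious adverse events by study arms during the course of prophylaxis". SAP 4.4.5 carries this through: "Incidence of adverse events and serious adverse events by study arms during the course of prophylaxis will be presented in the table 6a below".

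**Other end points.** Protocol section 8 has events documented "from the moment of drug administration in the study to discontinuation of the participant from study participation". Protocol 9.2.4 says "AE summaries will be generated for all AEs that occurred after study drug administration, until the end of the study", and SAP 4.4.5 repeats that sentence without defining the end of the study.

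**The concern.** The definition of an adverse event can expire while the participant is still taking assigned study drug. The safety endpoint is framed over the whole course, so an event on a late dosing day belongs to the endpoint but does not meet 8.1.1. Section 8 and 9.2.4 can be read as allowing it back in. Two people building SAP Table 6a from the same records could reach different counts.

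Section 8 says that the trial is meant to add to the safety evidence for artemether-lumefantrine (AL) as prophylaxis. The end of the weekly course is part of that exposure. The symptom questionnaire is given only at enrolment and follow-up visits, so nothing prompts a report after the last one.

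**Working it through.** This is a calendar count, with no power calculation involved.

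**Inputs**
- Dosing days: D0, D1, D2, then every seventh day from D7 (Appendix 2: 168 h, 336 h, weekly). Each AL dosing day is two doses.
- L = last forest day. Dosing is scheduled up to day L + 28 (6.5, 6.6).
- V = day of the last follow-up visit, D28 to D35 for a participant with one visit (6.6, 6.6.1, Appendix 1).
- Conventions: the visit named in 8.1.1 is the participant's last one, L is not after V, and a dose due on day V is taken before the visit.

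**The plan's own figure.** Section 6.6 gives 112 days in total: 3 × 28 + 28 = 112. With the third visit at D84, the plan itself schedules 112 − 84 = 28 days of prophylaxis after the last visit, with dosing days D91, D98, D105 and D112.

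**Formula.** Dosing days outside 8.1.1 = multiples of 7 that are greater than V and no greater than L + 28.

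| Last forest day L | Visit D28–D34 | Visit D35 |
|---|---|---|
| up to D6 | 0 | 0 |
| D7–D13 | 1 | 0 |
| D14–D20 | 2 | 1 |
| D21–D27 | 3 | 2 |
| D28–D34 (not after the visit) | 4 | 3 |
| D35 | – | 4 |

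**Illustrative early 10-day trip.** Departure is within 72 hours (5.5.2), so D0 to D3. Protocol 9.1 assumes at least 10 days per episode; placing them in one early trip is my assumption. L is then D9 to D13, and dosing ends between 9 + 28 = D37 and 13 + 28 = D41. The only weekly day after D28 and by D41 is D35. A visit on D28 to D34 leaves one dosing day outside, of eight in all (D0, 1, 2, 7, 14, 21, 28, 35). A visit on D35 leaves none.

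**Upper end.** With L = V, the interval from V to V + 28 always contains four weekly days. For V = 28 these are D35, D42, D49 and D56, which is 4 of 11 dosing days (36%) or eight AL doses. For V = 35 it is 4 of 12 (33%).

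**If the visit-day dose is taken after the visit.** This adds one where a dose falls due on the visit day, that is for a visit on D28 or D35. The early 10-day trip then gives 2 (D28) or 1 (D35), and leaving the forest on the visit day gives 5. For visits on D29 to D34 no dose is due that day and the counts stand.

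**Under the summary in 3.3.** That section puts the visit 28 ± 7 days after return. The earliest visit is at L + 21, so the tail is at most 28 − 21 = 7 days and one dosing day.

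**The case against.** **Later events may still be recorded.** Section 8 documents events until discontinuation from participation, and someone still on assigned drug has arguably not discontinued. Section 6.6.3 and Appendix 1 (last column, up to D112) follow confirmed malaria for a month after the last visit, so participation does not plainly stop there. Section 6.6.2 encourages participants to report symptoms at any time after enrolment. All of this stands. A reader might infer from 8.1.1 that late events will be lost; the documents do not support that. But section 8 also ties the investigator's duty to events meeting the protocol's definition, which leads back to 8.1.1. Its encouragement to report covers only the time between follow-up visits. The extension in 6.6.3 is for malaria and parasite genetics, not adverse events.

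**The SAP may already cover all dosing.** A reader might infer that SAP 4.4.5 contradicts itself, with one end point for the summaries and another for Table 6a. That holds only if the end of the study means the follow-up visit, as in 8.1.1. The SAP does not say so, and Protocol 7.1 uses the phrase for the whole trial. On that reading the summaries include every dose. What remains is an undefined term.

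**Visit timing in 3.3.** That summary would nearly close the gap. The operative text (6.6, 6.6.1, Appendix 1) times visits from the start of prophylaxis and should govern. The opening of section 6 might be taken to side with 3.3, but it gives no interval after return and refers to Appendix 1.

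**The effect is small.** True for many participants: an early short trip leaves one dosing day or none, and four requires leaving the forest on the day of the visit.

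**Conclusion.** The point holds as a conflict between a stated rule and the safety endpoint. Read literally, 8.1.1 excludes adverse events and SAEs on zero to four scheduled dosing days after the last visit, although 5.4.2 and SAP 4.4.5 count events over the course of prophylaxis. Other sections soften the rule without overriding it, so the risk is inconsistent counting of late on-drug events.

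The size rests on the conventions listed with the count. The documents do not give the distribution of last forest days, so the share of participants with one or more uncovered dosing days cannot be stated. If the visit in 8.1.1 were read as the first of three, twelve dosing days (D35 to D112) could fall outside. The wording does not require that reading, and I have not used it.

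A reader might also infer a biased safety comparison. The cut-off is the same in both arms, so the documents do not support that. The primary endpoint, power and sample size are unaffected. The change is worth making because it is cheap and concerns on-drug safety.

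**What to change.** - **One end point.** In Protocol 8, 8.1.1 and 9.2.4 and in SAP 4.4.5, end the adverse-event and SAE period at the later of the participant's last follow-up visit and last scheduled dose.
- **Capture.** Use the self-report route in 6.6.2 for events after the last visit, and extend the reporting encouragement in section 8 to the last dose. This matches the month of malaria capture after the last visit in 6.6.3 and Appendix 1. No extra visit is needed.
- **Reporting.** Show post-visit events separately in the SAP outputs, labelled as unprompted.
- **Visit timing.** Align the 3.3 summary with 6.6 and Appendix 1.

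**Cost.** A little more recording, one additional SAP output, and self-reported events that are open to reporting bias in an open-label trial, which is why they should be shown apart. The longer period cannot run into a re-randomised enrolment, because 6.6 requires at least 28 days after the last dose before re-enrolment.

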8.1.2 Serious Adverse Event

A serious adverse event is an AE that:

- results in death
- is life-threatening i.e. the participant was at risk of death at the time of the AE

- requires in participant hospitalisation or prolongation of existing hospitalisation
- results in persistent or significant disability/incapacity
- is a congenital anomaly/birth defect
- Any other significant medical condition

All of the above criteria apply to the case as a whole and should not be confused with the outcomes of individual reactions/events. More than one of the above criteria can be applicable to the one event. Important medical events that may not be immediately life-threatening or result in death or hospitalisation may be considered an SAE when, based upon appropriate medical judgment, they may jeopardise the participant or require medical or surgical intervention to prevent one of the outcomes listed in the definition above. Examples of such medical events include allergic bronchospasm requiring intensive treatment in an emergency room or at home, blood dyscrasias or convulsions that do not result in hospitalisation, or development of drug dependency or drug abuse.

8.2 Reporting Procedures for Serious Adverse Events

All SAEs must be reported by the site investigator to the Study PI and PAL-Cambodia safety and medical monitor, within one day of his or her awareness of the SAE. The SAE report, should be emailed to the email [contact].

Further reports should be submitted, if required, until the SAE is resolved.

The site investigator must also report the SAEs to the local ethics committee in accordance with local requirements.

8.3 Evaluating Adverse Events and Serious Adverse Events

8.3.1 Assessment of Intensity

Each adverse event will be graded according to the Common Terminology Criteria for Adverse Events (CTCAE) Version 5.0 November 2017.

If an adverse event is not listed in the CTCAE table, the Investigator will assess the severity using the following guidelines:

- 1 = Mild; asymptomatic or mild symptoms; clinical or diagnostic observations only; intervention not indicated.
- 2 = Moderate; minimal, local or noninvasive intervention indicated; limiting age appropriate instrumental ADL*
- 3 = Severe or medically significant but not immediately life-threatening; hospitalization or prolongation of hospitalization indicated; disabling; limiting self care ADL**
- 4 = Life-Threatening consequences; urgent intervention indicated
- 5 = Death related to AE

Activities of Daily Living (ADL)

*Instrumental ADL refer to preparing meals, shopping for groceries or clothes, using the telephone, managing money, etc.

**Self care ADL refer to bathing, dressing and undressing, feeding self, using the toilet, taking medications, and not bedridden.

8.3.2 Clarification of the difference in meaning between ‘severe’ and ‘serious’

The term “severe” is often used to describe the intensity (severity) of a specific event (as in mild, moderate, or severe myocardial infarction); the event itself, however, may be of relatively minor medical significance (such as severe headache). This is not the same as “serious”, which is based on the outcome or criteria defined under the serious adverse event definition. An event can be considered serious without being severe if it conforms to the seriousness criteria, similarly severe events that do not conform to the criteria are not necessarily serious. Seriousness (not severity) serves as a guide for defining regulatory reporting obligations.

8.3.3 Assessment of relatedness

The investigator is obligated to assess the relationship between study drug and the occurrence of each AE/SAE using the following categories of relatedness:

- Definite: clear-cut temporal association
- Probable: clear-cut temporal association, with improvement upon drug withdrawal, and not reasonably explained by the participant's known clinical state or other aetiology.
- Possible: less clear temporal association; other aetiologies are possible. (Other possible aetiologies should be recorded on the CRF).
- Not related: no temporal association with the study drug; assessed as related to other aetiologies such as concomitant medications or conditions, or participant's known clinical state.

The investigator will provide the assessment of causality as per the AE/SAE data collection tool.

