12.7 Incentives & Compensation

Study participants will be compensated for time lost from work as a result of trial activities, the cost of local transport to attend for the follow up visits and will receive a per diem to cover the costs of meals on those days. The amounts in monetary terms will be determined by CNM in accordance with local norms.

The study will pay for treatment for drug-related SAEs or other research-related injuries. The study cannot pay for long term care for disability resulting from complications of the illness.

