### Table 6c Adverse events by relationship to study drug

		AL				Multivitamin			
		Relationsh	nip to drug		Relationship to drug				
AE, n (%)	Unrelated	Probably	Possibly	Definitely	Unrelated	Probably	Possibly	Definitely	
Headache	XX (XX.X)	XX (XX.X)	XX (XX.X)	XX (XX.X)	XX (XX.X)	XX (XX.X)	XX (XX.X)	XX (XX.X)	
Loss of appetite	XX (XX.X)	XX (XX.X)	XX (XX.X)	XX (XX.X)	XX (XX.X)	XX (XX.X)	XX (XX.X)	XX (XX.X)	
Dizziness	XX (XX.X)	XX (XX.X)	XX (XX.X)	XX (XX.X)	XX (XX.X)	XX (XX.X)	XX (XX.X)	XX (XX.X)	
Fatigue	XX (XX.X)	XX (XX.X)	XX (XX.X)	XX (XX.X)	XX (XX.X)	XX (XX.X)	XX (XX.X)	XX (XX.X)	
Joint pain	XX (XX.X)	XX (XX.X)	XX (XX.X)	XX (XX.X)	XX (XX.X)	XX (XX.X)	XX (XX.X)	XX (XX.X)	

| Muscle pain    | XX (XX.X) |
|----------------|-----------|-----------|-----------|-----------|-----------|-----------|-----------|-----------|
| Abdominal pain | XX (XX.X) |
| Nausea         | XX (XX.X) |
| Vomiting       | XX (XX.X) |
| Diarrhoea      | XX (XX.X) |
| Itching        | XX (XX.X) |
| Cough          | XX (XX.X) |
| Fever          | XX (XX.X) |

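### The causality scale in Protocol 8.3.3 sets a weaker test for Definite than for Probable, so those two columns of SAP Table 6c cannot be read as ordered evidence

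*Protocol*

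**What the plan says.** Protocol 8.3.3 makes the scale compulsory: "The investigator is obligated to assess the relationship between study drug and the occurrence of each AE/SAE using the following categories of relatedness". It then lists four grades, in this order:

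- The top grade has one condition and no more: "Definite: clear-cut temporal association".
- The second grade has three conditions: "Probable: clear-cut temporal association, with improvement upon drug withdrawal, and not reasonably explained by the participant's known clinical state or other aetiology".
- The third grade rests on weaker timing: "Possible: less clear temporal association; other aetiologies are possible". Competing causes are to be written down when it is used.
- The bottom grade rests on absent timing and a different cause: "Not related: no temporal association with the study drug; assessed as related to other aetiologies such as concomitant medications or conditions". The entry also gives the person's own health status as an example of such a cause.

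The section ends by referring to an AE/SAE data collection tool, which is not among the documents. SAP 4.4.5 supplies no definitions of its own. It tabulates the grades by arm in Table 6c, "Adverse events by relationship to study drug", with columns in the order unrelated, probably, possibly, definitely. That is the only summary by relatedness that the SAP sets out.

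**The concern.** A causality scale is useful only if each step up demands more evidence than the step below. Here the top step drops two requirements that the next step imposes: that the event improved when the drug was withdrawn, and that nothing else reasonably explains it. The second is the question a causality assessment exists to answer. It matters in this population, because the AL effects listed in Protocol 12.4.1 (such as headache and dizziness) are also common complaints in intercurrent illness.

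The two lower grades do not rescue the scale. Each is tied to weaker timing or to none, so a clearly timed event with a competing cause has no natural place. Nor does a clearly timed event where the drug was never withdrawn, or one that was fatal or permanent and could not improve.

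At stake is how Table 6c is read. The protocol records adverse events in order to add to the safety evidence on AL as prophylaxis. A reader of the table would take the Definitely column as the firmest drug attribution, when by the written rule it may hold the least examined events.

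**Working it through.** There is no planned figure to reproduce. The check is of logic, followed by the reach of the grade.

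**1. Criteria.** The definitions use three criteria:

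- T: timing (clear-cut, less clear, none)
- W: improvement on withdrawal shown (yes or no, where no includes never withdrawn)
- E: another reasonable explanation (yes or no)

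That gives 3 × 2 × 2 = 12 profiles. Read literally:

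- Definite: T = clear-cut
- Probable: T = clear-cut and W = yes and E = no
- Possible: T = less clear, with other causes possible
- Not related: T = none, with the event attributed elsewhere

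**2. Matching.** The 2 × 2 × 2 = 8 profiles without clear-cut timing meet neither Definite nor Probable. The four with clear-cut timing are:

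| W | E | Definite | Probable | Possible | Not related |
|---|---|---|---|---|---|
| yes | no | meets | meets | no | no |
| yes | yes | meets | no | no | no |
| no | no | meets | no | no | no |
| no | yes | meets | no | no | no |

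So 4 of 4 meet Definite, 1 of 4 also meets Probable, and 3 of 4 meet Definite alone. Probable is a strict subset of Definite. Both profiles with another explanation fall in Definite alone. In the first row the text permits either grade and gives no rule for choosing.

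**3. How often clear timing might arise.** The documents do not say what counts as clear-cut, so only a range can be shown. Protocol Appendix 2 doses both arms on days 1, 2 and 3, then day 8 and weekly, so the dosing days in the first 28 are 1, 2, 3, 8, 15 and 22. Assume that the dosing day and the next k days count. The initial course covers 3 + k days and each of the three weekly doses covers 1 + k, so the total is (3 + k) + 3(1 + k) = 6 + 4k:

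| k | Days of 28 | Share |
|---|---|---|
| 0 | 6 | 21% |
| 1 | 10 | 36% |
| 2 | 14 | 50% |
| 3 | 18 | 64% |

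These are shares of calendar time under an assumed window, not shares of events.

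**4. What uses the grade.**

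| Item | Uses relatedness? |
|---|---|
| Definition of an adverse event (Protocol 8.1.1) | No; applies whether or not related |
| SAE reporting (Protocol 8 and 8.2) | No; all SAEs are reported |
| By-arm frequencies with Fisher's exact test (Protocol 9.2.3; p-values in SAP Table 6a) | No |
| Efficacy analyses (SAP 4.3, 4.4.1) | No |
| SAP Table 6c (no p-value column) | Yes |

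**The case against.** **The literal reading is not the only one.** The matching above treats each part of a definition as required. An investigator who attributes an event to another illness could lean on the part of Not related that speaks of attribution to other causes, or on the part of Possible that allows for them. The AE/SAE data collection tool may also carry fuller wording. This stands to the extent that one cannot say such an event must be graded Definite. It does not repair the scale: the timing part of both lower grades still conflicts with a clearly timed event, 8.3.3 presents its own list as obligatory, and individual departures from it would make grades vary between investigators who know the arm.

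**The line may be incomplete.** The Definite entry is the only one of the four without a closing full stop, so words may have been lost in drafting or in text extraction. That cannot be settled from the documents. If words are missing from the protocol itself, restoring them may be the whole remedy for that line.

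**Symptoms of a diagnosed illness would often not be graded separately.** Protocol 8 asks for a diagnosis rather than single symptoms where possible, so a headache during a malaria episode would normally be recorded as malaria. This reduces the number of awkward cases. It does not remove them, because the diagnosis itself has to be graded, and undiagnosed symptoms remain.

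**Two stronger inferences are tempting and are not supported.** A reader might infer that the trial's safety conclusion on AL is distorted. The randomised comparison of event frequencies ignores causality, and the documents state no stopping rule or endpoint that depends on it. A reader might also infer that payment is affected, since Protocol 12.7 says "The study will pay for treatment for drug-related SAEs or other research-related injuries". That section does not tie payment to the 8.3.3 grade, and it covers other research-related injuries as well. If it were tied, over-attribution would widen cover, not narrow it.

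**Conclusion.** The point holds as a minor error of wording: the text is wrong as written, not merely short of detail. Definite is easier to meet than Probable, and clearly timed events with a competing cause or without withdrawal information have no other clean grade. The consequence is confined to the Definitely and Probably columns of one descriptive table.

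The three-in-four result describes the logic of the definitions and says nothing about event frequency, which the documents do not allow one to estimate. The conclusion assumes that the printed list is what investigators apply and that the unseen data collection tool does not override it. If the tool holds a properly ordered scale, what remains is a mismatch between it and the protocol.

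**What to change.** Rewrite 8.3.3 so that the grades nest:

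- **Definite:** all the Probable criteria plus at least one stronger element, for example recurrence after a later dose where that happens to have been observed, or a confirmed drug-specific reaction. The choice of element is for the sponsor, and it should not alter how anyone is dosed.
- **Probable:** as now.
- **Possible:** any temporal association, clear or not, where another cause is also plausible.
- **Not related:** events better explained by another cause, whatever the timing.

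State how to grade a clearly timed event with no withdrawal information and no competing cause, since the present text leaves it only Definite. Bring the AE/SAE data collection tool into line, and order the columns of SAP Table 6c as unrelated, possible, probable, definite.

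The cost is a few lines in the protocol and in the tool's guidance, a change of column order, and a limited desk re-grade of any events already assessed. Because the trial is open-label, that re-grade should be done by someone unaware of the arm where feasible; otherwise it could add bias of its own.
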